7.2 Analyses

Statistical analyses will be conducted on an intent-to-treat population that includes all subjects who were enrolled and received study medication. Due to small sample size and exploratory nature of the study, descriptive statistics will be performed using SAS. Any additional statistical analyses will be performed as appropriate and detailed in the final report. All statistical tests will be two-sided and interpreted at a 5% significance level. Descriptive statistics (i.e., mean, standard deviation, etc.) will be provided for all continuous variables and frequencies for all categorical variables collected in this study. Summary tables will be used to present patient population characteristics at Baseline; data from the study questionnaires will be included. Analyses of study treatment will be performed using an ANCOVA technique with the Baseline value as the covariate provided the necessary assumptions for parametric tests are satisfied. The Wilcoxon Rank-Sum test will be used if the necessary assumptions for parametric tests are not satisfied. Mean scores will also be analyzed. Safety analyses will be performed in terms of incidence and severity of local tolerance signs and symptoms and adverse and/or unexpected events.

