1 STUDY OBJECTIVE

2 STUDY DESIGN

This will be a 3-center, open label study. 24 subjects will be enrolled. Target lesion will be identified on either the knees or elbows and evaluated for efficacy (TLSS) for the secondary endpoints at baseline, week 2 and week 4 (secondary). PGA will be recorded at baseline, week 2 and week 4 (primary endpoint). TLSS is expected to be a minimum score of 2 (moderate) for erythema, 2 (moderate) scaling, 2 (moderate) plaque thickness with overall score of 6. The study will consist of screening/baseline, week 2 & week 4. (3 visits). Adverse events will be recorded throughout study. Selected patient target lesions will be photographed at baseline, week 2 & week 4. Patients will be instructed to apply a 2 sec spray time per 1% BSA on plaques and instructed to wash their hands thoroughly after application.

Subjects will attend a Screening Visit/Baseline visit and if found eligible will be randomized to study treatment. Patients will be counselled on the use of the study medication and the medications will be labelled for the appropriate group as noted above. The duration of the study is 4 weeks and consists of a Screening/Baseline visit, and one (1) Follow-up Visit at Week 2 and end of treatment visit at week 4.

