3 SELECTION AND WITHDRAWAL OF SUBJECTS

3.1 Inclusion Criteria

Inclusion:

i. 1. Outpatient, male or female subjects of any race, 18 years of age or higher. Female subjects of childbearing potential must have a (-)UPT result at within 7 days of the first dose of study drug and practice a reliable method of contraception throughout the study;

A female is considered of childbearing potential unless she is:

- postmenopausal > 5Y, without a uterus and/or both ovaries; or has been surgically sterile for > 6M.

Reliable methods of contraception are:

- hormonal methods or IUD in use > 90d prior to study drug administration, barrier methods plus spermicide in use > 14d prior, or vasectomized partner.

[Exception: Female subjects of CBP who are not sexually active are not required to practice a reliable method of contraception and may be enrolled at the Investigator's discretion provided they are counselled to remain sexually inactive for the duration of the study and understand the risks involved in getting pregnant during the study.

- ii. Moderate plaque type psoriasis eligible for topical therapies.
- iii. Patients with a minimum of 3% BSA to a maximum of 20% BSA & bilateral symmetric psoriatic plaques of 2 to 4 cm in diameter
- iv. Physician Global Assessment (PGA) score of 3.
- v. Able to understand study requirements and sign Informed Consent/HIPAA forms.

Exclusion:

- i. Female subjects who are pregnant, breast-feeding, or who are of childbearing potential and not practicing a reliable method of birth control, or male subjects planning a pregnancy with their spouse or partner while in the study.
- ii. History of hypercalcaemia or vitamin D toxicity.
- iii. Patients with guttate, erythrodermic, or pustular psoriasis
- iv. Serious skin condition (other than psoriasis) or uncontrolled medical condition (in the opinion of the investigator).
- v. Topical steroids, topical immunomodulators, topical vitamin D derivatives, tar, salicylic acid, anthralin or any other topical treatment for psoriasis within 2 weeks of baseline.
- vi. Use of any biologics within 3 months of baseline.
- vii. Use of other systemic psoriasis treatments (ie, oral retinoids, methotrexate, cyclosporine, or other immunomodulators) within 4 weeks of baseline.
- viii. Use of UVB or PUVA within 2 weeks of baseline.
- ix. Skin conditions (e.g. eczema) psoriasis that may interfere with evaluations of psoriasis.
- x. Known hypersensitivity to Enstilar or any of its components.

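### The number of groups is not settled, and if the trial is one-arm the ANCOVA and Wilcoxon Rank-Sum test in Section 7.2 do not fit it

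*Combined protocol and SAP*

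**What the plan says.** Section 7.2 says that the study is small and exploratory, so descriptive statistics will be performed. It then names inferential methods: "Analyses of study treatment will be performed using an ANCOVA technique with the Baseline value as the covariate", conditional on parametric assumptions, and "The Wilcoxon Rank-Sum test will be used if the necessary assumptions for parametric tests are not satisfied". It adds: "All statistical tests will be two-sided and interpreted at a 5% significance level". It does not name a factor, a contrast or an endpoint for either method.

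On the design, Section 4.2.1 and the patient instructions at the end describe one product, once daily for four weeks, and Section 4.2.2 makes it open label. No comparator or allocation ratio appears. Against this:

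- Section 2 says that a subject "if found eligible will be randomized to study treatment", and that medication is labelled by group, pointing back to groups described earlier.
- Section 4.2.2 repeats that qualifying subjects are randomized and speaks of study treatments in the plural.
- Item e of the washout list counts back from randomization.

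Section 2 makes PGA the primary endpoint and TLSS secondary. Inclusion criterion iv (Section 3.1) requires a "Physician Global Assessment (PGA) score of 3", and screening and baseline are one visit.

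**The concern.** ANCOVA for a treatment effect needs at least two treatment levels, and Rank-Sum needs two independent samples. A one-arm trial in which every subject is measured at baseline, week 2 and week 4 supplies neither. Its natural question is change within subject, and its natural methods are paired or one-sample. Section 7.2 names none of these, yet it sets a 5% level for tests.

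If the methods are chosen after open-label data have been seen, the prespecified level loses its meaning. If Rank-Sum is simply run on baseline against week 4, its p-values are wrong in a direction that depends on the endpoint. A smaller point is that the one covariate named for adjustment cannot vary for the primary endpoint.

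**Working it through.** **Inputs.** n = 24 (Section 2) and n = 28 (Section 7.1) are both used; that discrepancy is a separate matter. Alpha is two-sided 5% (Section 7.2). Baseline PGA is 3 for every eligible subject (criterion iv, single screening/baseline visit). The plan gives no power, effect size, SD, correlation or PGA distribution, so there is no figure of its own to reproduce. The distributions below are assumptions.

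**1. What the model can estimate.** Rank of the design matrix, the same at n = 24 and n = 28:

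| Layout | Columns | Rank |
|---|---|---|
| PGA, one arm: intercept, baseline | 2 | 1 |
| PGA, two equal arms: intercept, baseline, group | 3 | 2 |
| TLSS (baseline varies), one arm: intercept, baseline, treatment | 3 | 2 |

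In rows 1 and 2 the constant baseline is aliased with the intercept and drops out. In row 2 the group effect is still estimable. In row 3 treatment is the aliased term: with one arm there is no treatment effect to fit.

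**2. Rank-Sum for PGA, one arm.** Assumed contrast: n baseline values, all 3, against n week-4 values. Assumed null: one-grade improvement and one-grade worsening each with probability q. Exact enumeration, with tie-corrected, continuity-corrected Rank-Sum:

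| q | Rank-Sum, n=24 | Rank-Sum, n=28 | Exact sign, n=24 | Exact sign, n=28 |
|---|---|---|---|---|
| 0.1 | 6.0% | 6.6% | 0.8% | 1.1% |
| 0.2 | 7.3% | 7.4% | 2.2% | 2.4% |
| 0.3 | 8.9% | 9.6% | 2.7% | 3.0% |

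A large-sample check explains the direction. With w worsening and i improving, U = n²/2 + n(w − i)/2, so its true variance is n²/4 × 2nq = n³q/2. The test uses about (n³/6)[1 − (1−q)³ − 2(q/2)³]. For q = 0.1, 0.2, 0.3, in units of n³, that is 0.0451, 0.0810, 0.1084 against true values 0.05, 0.10, 0.15. The ratios true/used are 1.11, 1.23, 1.38. Dividing 1.96 by their square roots gives 1.86, 1.76, 1.67, or sizes of about 6.3%, 7.8%, 9.6%.

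One case in full: n = 24, 4 improve by one grade, none worsen. U = 0.5 × 24 × 20 = 240 against 288 expected. Tie term = (4³ − 4) + (44³ − 44) = 85,200. Variance = (24 × 24/12)[49 − 85,200/(48 × 47)] = 539.2. z = (48 − 0.5)/√539.2 = 2.05, p = 0.041. The exact sign test gives 2 × 0.5⁴ = 0.125. With 5 improving, the p-values are 0.020 and 0.063; from 6 upward both tests reject.

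**3. Rank-Sum for TLSS and BSA, one arm.** Same assumed contrast, bivariate normal simulation (40,000 replicates), n = 24:

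| Assumed correlation | Rank-Sum size | Rank-Sum power, 0.5 SD shift | Signed-rank power, 0.5 SD shift |
|---|---|---|---|
| 0 | 4.8% | 38% | 35% |
| 0.3 | 2.1% | 35% | 48% |
| 0.5 | 0.8% | 34% | 62% |
| 0.7 | 0.1% | 31% | 83% |

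At n = 28 and correlation 0.5 the powers are 40% and 70%. At a 1 SD shift the gap nearly closes: 94% to 99% against 97% to 100% at n = 24, over correlations 0.3 to 0.7.

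**4. Two independent groups.** Rank-Sum between groups on week-4 PGA, same null: size 2.7%, 4.5%, 4.5% at 12 per arm and 4.1%, 4.4%, 4.6% at 14 per arm. There is no inflation.

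**The case against.** The strongest reply is that the number of groups is open. The document refers to randomization several times, and some front matter was not available for this review and may define groups. With two independent groups, the named methods work. This stands: the misfit is conditional on a one-arm design, and it would be wrong to infer that the trial is certainly one-arm or that its analysis certainly cannot be run. A within-patient comparison cannot be excluded either. Criterion iii asks for "bilateral symmetric psoriatic plaques of 2 to 4 cm in diameter", although Section 2 says only that a "Target lesion will be identified on either the knees or elbows".

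Second, the plan never commits to comparing baseline with week 4 by Rank-Sum. Also true. The sizes and powers show what would follow from the most natural use of the test in one arm; they do not describe a test that the plan specifies.

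Third, ANCOVA is conditional on its assumptions, and PGA, an ordinal grade, may never enter it. In one arm, regressing change in TLSS or BSA on centred baseline would leave an intercept that tests mean change. Both are fair, but Section 7.2 specifies no such model, and its stated fallback is Rank-Sum.

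A reader might infer that the constant covariate biases the primary analysis, or that Rank-Sum raises false positives throughout. Neither is supported. The covariate drops out harmlessly, and for TLSS and BSA the error is conservative when the correlation is positive.

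Finally, this is a pilot with descriptive aims. That limits the impact, but does not remove the named tests or their 5% level.

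**Conclusion.** The point holds in conditional form. What the visible text establishes is that the passages on treatment, randomization and groups disagree, and that Section 7.2 gives no contrast to resolve them. If the trial is one-arm, the named ANCOVA and Rank-Sum do not match the design. Under the assumed contrast and distributions, Rank-Sum would then be modestly liberal for PGA and would lose power for small TLSS and BSA changes. If two independent groups exist, only the minor point remains: the baseline covariate does nothing for PGA.

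The harm is confined to p-values and significance statements. Means and frequencies are unaffected, and large effects are detected either way. It should be corrected before analysis because the correction is cheap, not because the descriptive results are in danger.

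**What to change.** State the number of groups and the contrast, and reconcile Sections 2, 4.2.1 and 4.2.2 and item e of the washout list.

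- **If one-arm:** remove the randomization and group wording from Sections 2 and 4.2.2, and align the reference to randomization in washout item e without changing the washout itself. Replace the ANCOVA and Rank-Sum sentences along these lines: *TLSS and BSA will be summarised as mean change from baseline with a paired-t 95% confidence interval, or analysed by Wilcoxon signed-rank if assumptions fail. Week-4 PGA will be summarised by frequencies and the proportion improved from 3 with an exact 95% confidence interval; any test will be a one-sample test of change from 3 (exact sign or signed-rank, to be named in advance).*
- **If two independent groups:** describe them and their allocation, keep ANCOVA/Rank-Sum for TLSS and BSA, and compare week-4 PGA between groups without the baseline covariate.
- **If within-patient:** describe the comparison and use paired methods.

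**Cost.** For one arm, this is wording only, with no extra patients, visits or data. The price is power for PGA: at n = 24, with an assumed 5% worsening and 35% or 50% improving one grade, the exact sign test has 58% or 87% power, against 78% or 95% for Rank-Sum. That comparison is not size-matched, since Rank-Sum gains partly by exceeding 5%. The sign test also ignores how many grades a subject improves, one reason to lead with the estimate and its interval. If a second group is intended, its description and allocation must be added, which is more than wording.

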8 RESPONSIBILITIES OF THE INVESTIGATOR

8.1 Good Clinical Practice

Investigators must adhere to the procedures outlined in this Study Protocol. The procedures set out in this study protocol, pertaining to the conduct, evaluation, and documentation of this study, are designed to ensure that the Investigator abides by GCP as described in the ICH Guidelines Topic E6: "Guideline for Good Clinical Practice." Compliance with these regulations also constitutes compliance with the ethical principles described in the current revision of the Declaration of Helsinki. The study will also be carried out in keeping with local legal and regulatory requirements.

8.2 Ethics

The appropriate IRB must review the Study Protocol and Informed Consent Form prior to initiating the study. Any significant modifications to the IRB-approved protocol or informed consent must be made in consultation with the IRB.

8.3 Confidentiality of Subjects

Any information that identifies subjects with respect to this research study will be kept confidential. However, records identifying the subject may be inspected by representatives of the IRB and/or the FDA. Subjects' identity will remain strictly confidential during all record reviews, as well as in any publication that may result from this research. Subjects will be identified by study code only; their names will not be used.

8.4 Informed Consent

Informed consent is a process that is initiated prior to the individual's agreeing to participate in the study and continuing throughout the individual's study participation. Appropriate discussion of risks and possible benefits of this therapy will be provided to the subjects. Consent forms describing in

detail the study interventions/products, study procedures and risks will be given to the subject and written documentation of informed consent is required prior to starting intervention/administration study product.

Consent forms will be IRB approved and the subject will be asked to read and review the document. Upon reviewing the document, the investigator will explain the research study to the subject and answer any questions that may arise. The subjects will sign the informed consent document prior to any procedures being done specifically for the study. The subjects should have the opportunity to discuss the study with their surrogates or think about it prior to agreeing to participate. The subjects may withdraw consent at any time throughout the course of the trial. A copy of the informed consent document will be given to the subjects for their records. The rights and welfare of the subjects will be protected by emphasizing to them that the quality of their medical care will not be adversely affected if they decline to participate in this study.

8.5 Data Handling and Record Keeping

Investigators must ensure that proper source documentation for all study activities are diligently maintained and securely kept. Investigators will transfer all relevant data from source documents to the Case Report Form as stipulated in this Study Protocol and his/her signature on the Case Report Form guarantees completeness and integrity of these data. Investigators will maintain reliable study device dispensing/dosing records and will store study supplies in a secure, locked location. In addition, Investigators will ensure that all study-related source documentation and Case Report Forms will be maintained for a period of two years after the conclusion of the study.

8.6 Direct Access to Source Data/Documents

Investigators must ensure that the Informed Consent Form clearly permit study-related monitoring, audits, IRB review, and regulatory inspections providing direct access to source data and documents.

Physicians Global Assessment Psoriasis O. Clear: no signs of psoriasis (Hyper/hypopigmentation changes alone are acceptable). Plaque elevation = 0. Scaling = 0. Erythema = +/- (hyperpigmentation, pigmented macules,

diffuse faint pink or red coloration).

- ____1. Almost Clear: Plaque elevation = +/- (possible but difficult to ascertain whether there is slight elevation above normal skin). Scaling = +/- (surface dryness with some white discoloration). Erythema = up to moderate (up to definite red coloration).
- 2. Mild: Plaque elevation = slight (slight but definite elevation, typically edges are indistinct or sloped). Scaling = fine (fine scale partially or mostly covering lesions). Erythema = up to moderate (up to definite red coloration).
- ____ 3. Moderate: Plaque elevation = moderate (moderate elevation with rough or sloped edges). Scaling = coarse (coarse scale covering most or all of the lesions). Erythema = moderate (definite red coloration).
- 4.Severe: Plaque elevation = marked (marked elevation typically with hard or sharp edges). Scaling = coarse (coarse, nontenacious scale predominates, covering most of all lesions). Erythema = severe (very bright red coloration).
- 5. Very Severe: Plaque elevation = very marked (very marked elevation typically with hard, sharp edges). Scaling = very coarse (coarse, thick, tenacious scale over most of all lesions; rough surface). Erythema = very severe (extreme red coloration; dusky to deep red coloration).

Washout for Psoriasis Medications

- a. Topical immunomodulators, topical vitamin D derivatives, tar, salicylic acid, anthralin or any other topical treatment for psoriasis except topical corticosteroids that they are already using within 2 weeks of baseline.
- b. Use of any biologics within 3 months baseline
- c. Use of other systemic psoriasis treatments (ie, oral retinoids, methotrexate, cyclosporine, or other immunomodulators) within 4 weeks of baseline.
- d. Use of UVB or PUVA within 2 weeks of baseline.
- e. Use of any investigational drug within 4 weeks prior to randomization, or 5 pharmacokinetic/pharmacodynamic half lives, if known (whichever is longer)

PSORIATIC BODY SURFACE AREA

BODY AREA	% of BODY AREA AFFECTED	% of TOTAL BODY SURFACE AREA	% of TOTAL BODY SURFACE AFFECTED
HEAD		10%	
TRUNK		30%	
UPPER LIMBS		20%	
LOWER LIMBS		40%	
TOTAL		100%	

(Multiply the numerical percent of the body part affected x the % of the total body surface area for each body area. Then add the % of total body surface affected for each area to determine the total BSA. For example: If the % of the head affected is 10, multiply ten by the % of total body surface area (10% = 0.1) for a total of 1% of Total Body Surface Area.)

PHYSICIAN EVALUATION OF TARGET PSORIASIS LESION

Mark location of target plaque loca	ation and size:
Erythema	
Induration	
Scaling	
	Sum of scores
Definition:	
Erythema : $0 = \text{no evidence of eryt}$	thema
2 = pink coloration	
4 = red coloration	
6 = very red coloration	
8 = extreme red colorat	tion
Induration: 0 = no evidence of pla	ague above normal skin level
	vation, above the normal skin level
4 = Moderate elevatio	on with rounded or sloped edges to plaque
6 = Marked elevation	with hard sharp edges to plaque
	ation with very hard sharp edges to plaque
	1 5 1 1
Scaling: 0 = No evidence of scaling	g on the legion
2 = Mild mainly fine scale	es some lesion at least partially covered
4 = Moderate somewhat of	oarser scale most lesion at least partially covered
6 = Severe coarse thick see	ales virtually all lesion covered rough surface
8 = Very severe coarse ver	ry thick scales all lesion covered rough surface

ENSTILAR PATIENT INSTRUCTIONS

Instruct patients to shake can prior to using Enstilar® Foam and to wash their hands after applying the product. Apply Enstilar® Foam to affected areas once daily for 4 weeks. Rub in Enstilar® Foam gently. Discontinue use when control is achieved. Instruct patients not to use more than 60 g every 4 days. Enstilar® Foam should not be used with occlusive dressings unless directed by a physician. Enstilar® Foam is not for oral, ophthalmic, or intravaginal use. Avoid use on the face, groin, or axillae, or if skin atrophy is present at the treatment site

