4.2 Study Treatment

4.2.1 Details of Study Treatment

Enstilar® Foam is a white to off-white opalescent liquid in a pressurized aluminum spray can with a continuous valve and actuator. At administration the product is a white to off-white foam after evaporation of the propellants. Each gram of Enstilar® Foam contains 52.2 mcg calcipotriene

hydrate (equivalent to 50 mcg of calcipotriene) and 0.643 mg of betamethasone dipropionate (equivalent to 0.5 mg of betamethasone).

Enstilar® Foam contains calcipotriene hydrate and betamethasone dipropionate. It is intended for topical use only. Calcipotriene hydrate is a synthetic vitamin D3 analog. Chemically, calcipotriene hydrate is 9.10-secochola-5.7.10(19),22-tetraene-1,3,24-triol,24-cyclo-propylmonohydrate, (1a,3ß,5Z,7E,22E,24S) with the empirical formula C27H40O3,H20, a molecular weight of 430.6, Calcipotriene hydrate is a white to almost white, crystalline compound. Betamethasone dipropionate is a synthetic corticosteroid. Betamethasone dipropionate has the chemical name pregna-1,4-diene-3,20-dione-9-fluoro-11-hydroxy-16-methyl-17,21-bis(1 oxypropoxy)-(11β,16β), with the empirical formula C28H37FO7, a molecular weight of 504.6, a: Betamethasone dipropionate is a white to almost white crystalline powder. Enstilar® Foam is a white to off-white opalescent liquid in a pressurized aluminum spray can with a continuous valve and actuator. The propellants used in Enstilar® Foam are dimethyl ether and butane. At administration the product is a white to off-white foam after evaporation of the propellants. Each gram of Enstilar® Foam contains 52.2 mcg calcipotriene hydrate (equivalent to 50 mcg of calcipotriene) and 0.643 mg of betamethasone dipropionate (equivalent to 0.5 mg of betamethasone) in a base of white petrolatum, PPG-11 stearyl ether, mineral oil, all-rac-alphatocopherol, and butylhydroxytoluene.

Dispensation and Dosage Schedule

A 4-week supply of study medication will be dispensed at baseline and applied daily from weeks 0 to week 4. Subjects will be instructed to apply study medication once per day per supplement II.

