4.2.5 Treatment Compliance

Subject compliance to study treatment regimen will be assessed at each visit; study personnel will ask each subject whether they missed any applications of study medication since the previous visit.

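### Section 4.2.1 has drug applied daily to week 4, but the patient instructions also say to stop on control, so the week-4 PGA can mix subjects on and off drug

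*Combined protocol and SAP*

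**What the plan says.** Section 4.2.1 (Dispensation and Dosage Schedule) sets a fixed course: "A 4-week supply of study medication will be dispensed at baseline and applied daily from weeks 0 to week 4". It makes no provision for stopping early and refers to a supplement for the method: "Subjects will be instructed to apply study medication once per day per supplement II". No part of the document carries that label. The only instructions for subjects are the Enstilar Patient Instructions on the last page. These first give a fixed course, "Apply Enstilar® Foam to affected areas once daily for 4 weeks", and two sentences later an open-ended one, "Discontinue use when control is achieved".

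Section 2 gives the endpoint as "PGA will be recorded at baseline, week 2 and week 4 (primary endpoint" and describes the later visits as "one (1) Follow-up Visit at Week 2 and end of treatment visit at week 4". Section 7.2 analyses everyone enrolled who received study medication. On adherence, section 4.2.5 provides that "study personnel will ask each subject whether they missed any applications of study medication since the previous visit". Sections 4.1.1 and 4.2.4 add drug accountability at each visit and records of quantities dispensed and returned.

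**The concern.** A subject who responds well by week 2 is told by one text to keep applying drug and by the other to stop. Control is not tied to a PGA or TLSS value, no one is named to judge it, and nothing is said about restarting. PGA 0, PGA 1 or the subject's own opinion would all fit the wording, and the three centers have no common rule.

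What is at stake is the meaning of the week-4 PGA. Under continued daily use it describes four weeks of treatment. Under a stop on control it describes treatment until response and then whatever follows. These are different quantities. The subjects who move from one to the other are not a random subset: they stop because they have responded. If any of them worsen after stopping, their week-4 score is worse than their best response, and the primary summary moves with it. Week-4 TLSS and BSA are exposed in the same way. Only one treatment is described, so there is no comparison arm in which the effect might cancel.

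**Working it through.** The plan gives no figure on this point, so there is none to reproduce. The check is a comparison of texts, followed by a short illustration.

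**Comparison of texts**

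1. *Duration.* Section 4.2.1: daily, week 0 to week 4, no exception. Patient instructions: daily for four weeks, and also stop on control. Neither text says up to four weeks. The two rules agree only for a subject who never reaches control before week 4.
2. *Link between the texts.* That the patient instructions are the supplement cited in 4.2.1 is an inference; they are the only candidate. The conflict does not depend on it, because the instructions carry both rules themselves.
3. *Does the subject leave the study?* Section 3.3 lists the circumstances for discontinuation: a disabling serious adverse event, intolerance, an emerging exclusion criterion, and voluntary withdrawal. Stopping drug for control is not among them, so the subject remains and attends week 4.
4. *Does the subject leave the analysis?* No. Section 7.2 includes all enrolled and treated subjects. It has no rule for those who stopped drug early.
5. *Which time point?* In section 2 the primary-endpoint tag follows week 4, and that visit ends treatment. Week 4 is the natural reading, although section 7.2 does not restate it.
6. *Can the groups be told apart?* Section 4.2.5 asks about missed applications but does not say how an instructed stop is to be coded. Returned quantities (4.2.4) help only roughly. Use depends on treated area (section 2 sets spray time per 1% BSA, and section 3.1 admits 3% to 20% BSA), and the area shrinks as plaques clear. A light can or a full one therefore does not give a stop date. No date of last application and no reason for stopping is specified.

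**Illustration of how easily mixing could arise**

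The documents give no rate of early control, so *p*, the share of subjects who stop for control before week 4, is assumed. Subjects are taken as independent. Section 2 gives n = 24 and section 7.1 gives n = 28, so both are shown.

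Expected number off drug at week 4 = n × p. Chance of at least one = 1 − (1 − p)^n.

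| Assumed p | Expected off drug, n = 24 / 28 | Chance of at least one, n = 24 / 28 |
|---|---|---|
| 5% | 1.2 / 1.4 | 1 − 0.95^24 = 71% / 1 − 0.95^28 = 76% |
| 10% | 2.4 / 2.8 | 92% / 95% |
| 25% | 6.0 / 7.0 | above 99% for both |

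Even a low early-control rate would probably leave at least one subject off drug at week 4. The table says nothing about how far the PGA summary would shift. That also needs the change in PGA after stopping, which the documents do not give.

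**The case against.** The strongest reply is that this is an open-label, descriptive pilot with no formal sample size, that section 7.2 already keeps every treated subject, and that nothing shows anyone will stop early. Much of that stands. Mixing is a possibility and not a stated fact. The analysis set already fits a summary that ignores whether drug is still being applied; what is missing is the statement that this is intended. No powered decision depends on the result.

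Several stronger readings are tempting, and the documents do not support them:

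- *That the primary result falls by a given amount.* A reader might assume that 10% to 40% stop early and that 10% to 50% of those lose control by week 4, giving 0.10 × 0.10 = 1 point to 0.40 × 0.50 = 20 points. Both ranges are invented, and the sum supposes that everyone who lost control would have kept it on daily drug. It also needs a responder rate, whereas the plan has a 0 to 5 PGA scale and descriptive summaries, with no responder definition.
- *That the groups could never be separated.* Accountability records and the missed-application question allow a partial separation.
- *That an instructed stop will be counted as non-compliance.* Section 4.2.5 fixes the question, not the coding. It may happen.
- *That nothing else would be learned.* PGA, TLSS and BSA are also recorded at week 2, and safety is summarised.
- *That the centers do read the text differently.* Nothing shows that they do; the text only leaves room for it.

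What the reply does not remove is the conflict itself. A descriptive week-4 PGA is useful only if the reader knows which regimen it describes.

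**Conclusion.** The point holds as an internal contradiction that reaches the primary endpoint. A subject controlled before week 4 cannot comply with both instructions, remains in the study and the analysis, and is scored at week 4. The primary result can then combine subjects on and off drug, with the off-drug group selected by response, and the data specified would separate them only in part.

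The size cannot be stated, because stopping rate, relapse rate and responder definition are all absent. The direction is conditional: worsening after a stop would make the week-4 result look less favourable than continued daily use would have. The conclusion rests on reading week 4 as the primary time point and on section 3.3 not treating a stop for control as withdrawal. It should be fixed, but in a descriptive pilot it does not by itself invalidate the study.

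**What to change.** 1. Reconcile section 4.2.1 and the patient instructions so that all sites and subjects work to one rule, and label the instructions so that the cross-reference resolves. Which rule to keep is for the sponsor's clinical team. If the retained rule refers to control, that team should also say what it means and who judges it.
2. Record the date of last application and the reason for stopping, so that an instructed stop can be told apart from missed doses.
3. State in section 7.2 that the primary summary is the week-4 PGA in all treated subjects, whether or not they are still applying drug, and report the number who stopped early for control.
4. Treat any breakdown of week-4 PGA by still applying versus stopped as descriptive only. The groups are defined by response, so a difference between them is not an effect of stopping.

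The cost is one wording amendment, one or two data fields and one line in a table. No visits or subjects are added. The date and reason should be in place before enrolment, since they are hard to recover afterwards.
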